112 smell. If this is true, it suggests that there is an odor signature of hypoglycemia that is detected by dogs, and
113 that this odor signature might also be detected by previously developed nose-like nanosensing technology. A
114 hypoglycemia detecting nanosensor or nanosensor array could be built into a compact, non-invasive warning
115 system that could be employed by diabetics to detect incipient hypoglycemia. Such a system might be
116 particularly useful in the form of a bedside device or one that would be installed in an automobile.

117
118 **I.b. Bionic Pancreas System**

119 We have developed an autonomous, self-learning BP that requires only the subject's weight for initialization, and
120 then autonomously adapts, modestly or dramatically, as needed, to cope with the wide range of insulin
121 requirements of adults, adolescents, and pre-adolescents with T1D, and potentially for patients with insulin
122 dependent type 2 diabetes. The BP obviates the need for the patient to know, or even appreciate, their insulin
123 requirements, and renders obsolete any need for patients or caregivers to know carbohydrate-to-insulin ratios,
124 basal rates, or insulin correction factors.

125
126 Our core technology is the insulin controller, which orchestrates all subcutaneous (SC) insulin dosing. At its
127 centerpiece is a model-predictive control (MPC) algorithm, which bases insulin doses on the glucose data and
128 insulin absorption kinetics. We were the first to incorporate insulin pharmacokinetics (PK) into the algorithm, by
129 augmenting it with a mathematical formulation for estimating the concentration of insulin in the blood and
130 predicting its future concentration. It is essential to compensate for the slow absorption rate of SC insulin analogs
131 (peak time in blood of 30--90 min, clearance in 4--8 hr), and to enable the algorithm to refrain from stacking and
132 overdosing insulin. Furthermore, the MPC algorithm automatically adjusts its insulin-dosing aggressiveness
133 continuously and in real-time to different insulin needs between individuals and variable needs within the same

134 individual. Running in parallel with the MPC algorithm is an algorithm that automatically modulates basal insulin
135 delivery over multiple time scales, and another algorithm that automatically adapts insulin doses in response to
136 optional meal announcements. Unlike current insulin pumps, and all of the insulin-only control algorithms of

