771 to move faster than a comfortable walking pace. Subjects will be reminded that the goal is not to raise

772 their heart rate or sweat, but to keep moving and keep their leg and core muscles activated without
773 excessive exertion.

774 • Subjects will continue walking until the hypoglycemia threshold has been reached, or up to 1 hour.
775 Exercise will be terminated when:

- 776 ○ Subjects reach a PG of 50 mg/dl or lower
- 777 ○ Subjects reach a PG of < 60 mg/dl but > 50 mg/dl for three consecutive measurements taken
778 every 5 minutes and thereafter choose to treat with oral carbohydrates (subjects may elect not
779 to treat hypoglycemia with carbohydrates if the PG is >50 mg/dl)
- 780 ○ They have completed 1 hour of walking with no treatment for hypoglycemia

781 • During exercise, BG measurements using the YSI will be obtained according to the following protocol:

- 782 ○ If PG is ≥ 80 mg/dl, BG measurements will be obtained off of the IV line every 10 minutes
- 783 ○ If the PG is < 80 mg/dl, BG measurements will be obtained off of the IV line every 5 minutes.
- 784 ○ If PG is <60 mg/dL for more than three consecutive measurements but is still > 50 mg/dl, subjects
785 will have the option to treat with carbohydrates, and if subjects choose to treat exercise will be
786 terminated.
- 787 ○ If PG is < 50 mg/dL, exercise will be terminated and subjects will be required to treat with
788 carbohydrates.
 - 789 ▪ Carbohydrates will be given according to the following protocol: Dextrose (g) = BSA
790 (m^2)/[1.7 m^2 (women) or 1.9 m^2 (men)] *15g
 - 791 ▪ Repeat treatments will be given at 15 minute intervals as long as hypoglycemia continues
- 792 ○ If the YSI fails, the Nova StatStrip Xpress meter will be used for glucose measurements.

793 • Study staff will collect samples of sweat from the subject's underarm and will ask subjects to exhale into
794 a breath collection device at the beginning of, at intervals during, and at the completion of exercise, with
795 increased frequency during any episodes of hypoglycemia. These samples will be collected, de-identified
796 and shipped out to collaborators at the MITRE Corporation for analysis of the relationship between
797 volatile organic compounds in breath and sweat and hypoglycemia.

798 • PG monitoring off of the IV line will continue after the exercise is completed or stopped according to the
799 following protocol:

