- 800 ○ If the PG is ≥ 120 mg/dl, BG measurements will be obtained off of the IV line every 20 minutes.
- 801 ○ If PG is 80-119 mg/dl, BG measurements will be obtained off of the IV line every 10 minutes
- 802 ○ If PG is < 80 mg/dl, BG measurements will be obtained off of the IV line every 5 minutes

[figure not shown]
803 • If the subject reached the hypoglycemia threshold during exercise, their PG will continue to be monitored
804 after exercise is stopped. They will be discharged from the DRC when they have maintained a PG ≥ 70
805 mg/dl for 1 hour. In this scenario the end of this hour will be the end of the post-exercise monitoring
806 period. They will be allowed to treat with oral carbohydrates at their discretion during this time to
807 maintain their blood glucose.

808 • If the subject did not reach the hypoglycemia threshold during exercise, they will be monitored for an
809 additional 30 minutes after exercise is stopped.

- 810 ○ If they reach the hypoglycemia threshold during this additional 30 minutes, they will continue to
811 be monitored until they maintain a PG ≥ 70 mg/dl for 1 hour. In this scenario the end of this hour
812 will be the end of the exercise and post-exercise monitoring period. They will be allowed to treat
813 with oral carbohydrates at their discretion during this time to maintain their blood glucose.
- 814 ○ If they do not reach the hypoglycemia threshold during this additional 30 minutes, this will
815 complete the post-exercise monitoring period.
- 816 ○ After the post-exercise monitoring period is completed, a correction bolus of insulin will be given
817 via syringe.
 - 818 ▪ This dose of insulin will be calculated using their own correction factor, correcting them
819 down to a PG of 50 mg/dl using their current PG.
 - 820 ▪ The PG will continue to be monitored after the insulin injection is given and
821 hypoglycemia will be treated per protocol.

822
823
824
825
826
827
828
829
830
831
832
833

- If the subject reaches the hypoglycemia threshold following the insulin injection, they will be monitored until they maintain a PG \geq 70 mg/dl for 1 hour
- If the subject does not reach the hypoglycemia threshold, after two hours, they will be discharged
- Once the post-exercise monitoring is complete and the subject's plasma glucose is stable, they will be discharged off of the bionic pancreas.
 - Their glucose meters and bionic pancreas will be downloaded.

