1019 from periods when the bionic pancreas was not in use, if available (Dexcom CGM data may not be available in
1020 some failure modes). In cases where an arm was not completed we will use the available data from that arm in
1021 the data analysis. We will calculate percentages, means standard deviations (and medians and interquartile
1022 ranges as appropriate), and ranges in descriptive analyses. We will use the Shapiro-Wilk test to determine
1023 normality of the variables. We will use paired t-test for comparison of means for normally distributed
1024 outcomes and the Wilcoxon Signed Rank test for comparisons on non-normally distributed outcomes. In a
1025 secondary analysis we will look for any period effect in normally distributed outcomes and any interaction
1026 between treatment and period, although no such interaction is predicted and there is probably insufficient
1027 power to identify a small interaction. We may, in exploratory analyses, also stratify subjects for secondary
1028 analyses of the pre-specified endpoints by the following characteristics: sex, age, usual care insulin total daily
1029 dose, body mass index, baseline A1c, and use of CGM in usual care.

1030
1031 **VI. c. Power Analysis**

1032 **Power Calculation for Aim 1**

1033 The sample size for this study is being based on the power calculations for Aim 1. From our clinical experience,
1034 we expect the hypoglycemia rate to be around 25% in the bi-hormonal arm and around 75% in the insulin-only
1035 arm, corresponding to a difference of 50 percentage points.

1036 The table below provides power calculations of a two-sided exact McNemar's test with 2.5% type I error under
1037 varying degrees of within-subject correlations.

1038 Based on our clinical experience with bi-hormonal bionic pancreas, patients who develop hypoglycemia using bi-
1039 hormonal bionic pancreas are highly likely to also develop hypoglycemia when not given glucagon. We expect
1040 5% of patients who develop hypoglycemia with glucagon will have no hypoglycemia when glucagon is not given.
1041 If our expectation is correct, our planned sample size of 20 patients will provide ≥90% statistical power to detect
1042 a difference in hypoglycemia rates between the two arms. If this proportion is three times as big as we expect
1043 (15%), we will still have 82% power to detect the difference.

1044

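### A subject given syringe insulin aimed at PG 50 mg/dl who misses the hypoglycemia threshold may leave at two hours on an unquantified stable PG, while the other three exits require PG ≥70 mg/dl for 1 hour

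*Combined protocol and SAP*

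**What the plan says.** Section V.d.v, Exercise Visits, gives four ways out of the visit.

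- **Threshold reached during exercise:** PG ≥70 mg/dl maintained for 1 hour.
- **Threshold reached in the following 30 minutes:** the same rule. In both of these exits oral carbohydrate is permitted once the threshold has been reached: "They will be allowed to treat with oral carbohydrates at their discretion during this time to" maintain glucose.
- **Threshold reached after the syringe dose:** "If the subject reaches the hypoglycemia threshold following the insulin injection, they will be monitored until they maintain a PG" of at least 70 mg/dl for 1 hour.
- **Syringe dose given, threshold not reached:** "If the subject does not reach the hypoglycemia threshold, after two hours, they will be discharged".

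The syringe dose uses the subject's own correction factor to bring them "down to a PG of 50 mg/dl using their current PG". A general condition covers all exits: once monitoring is complete and the subject's "plasma glucose is stable, they will be discharged off of the bionic pancreas". No level, duration or slope defines stable.

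The hypoglycemia threshold is not formally defined. The exercise stopping rules in the same section imply it: PG of 50 mg/dl or lower, or "Subjects reach a PG of < 60 mg/dl but > 50 mg/dl for three consecutive measurements taken" every 5 minutes. Section I.b describes subcutaneous insulin as having a "peak time in blood of 30--90 min, clearance in 4--8 hr), and to enable the algorithm to refrain from stacking and" overdosing.

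**The concern.** The written floor is weakest where extra insulin has been given. Subjects in the first two exits receive no syringe dose, yet must hold 70 mg/dl for an hour. A subject in the fourth exit has received insulin aimed at 50 mg/dl, is fasted and has just exercised, and needs no stated level. A steady PG of 60–69 mg/dl does not reach the threshold, triggers no treatment and can fairly be called stable. At stake is safety after discharge at a small number of visits, with part of the dose possibly still acting.

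The handover is also uneven. The review of recent dosing is written only for subjects returning to their own pump. A same-day restarter repeats the Visit 1 procedures, where the controller is initialized with weight alone. No written step passes on the syringe dose, although the site staff who gave it will know of it.

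**Working it through.** The plan gives no figure for this point, so there is nothing to reproduce. The check has three parts.

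**1. Does a steady 60–69 pass the written rule?** Take flat traces over two hours at the 5-minute spacing used below 80 mg/dl (25 readings). Test them against every reading of the threshold that the text allows: ≤50; <60 on three consecutive readings; <60 on more than three; any <60.

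| Flat PG (mg/dl) | Threshold reached? | ≥70 for 1 hour? | Fourth exit open? |
|---|---|---|---|
| 51, 55, 59 | yes, except under ≤50 only | no | only under ≤50 |
| 60, 65, 69 | no, under all four | no | yes |
| 70 | no, under all four | yes | yes |

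So 60–69 passes under every reading, and the rule used in the other three exits would hold it.

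**2. How many visits?** There are 20 subjects × 2 visits = 40. In section VI.c, "we expect the hypoglycemia rate to be around 25% in the bi-hormonal arm and around 75% in the insulin-only" arm.

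- Visits with an event: 20×0.25 + 20×0.75 = 5 + 15 = 20.
- Visits with a syringe dose: 40 − 20 = 20, of which 15 are bi-hormonal and 5 insulin-only.
- The Aim 2 power section expects at least 30 visits with hypoglycemia and 30–40 episodes. The fourth exit is left with 40 − 30 = 10 down to 40 − 40 = 0 visits.

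These counts are approximate, because the event definitions differ between sections.

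**3. Illustration of what the fourth exit could look like.** The protocol does not give PG at injection or an insulin action curve, so both are assumed. Further assumptions: an accurate correction factor, no food, no glucagon and no change in pump insulin. With r the fraction of the dose still to act at two hours,

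PG(2 h) = 50 + (PG₀ − 50) × r.

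- Two-compartment curve, r = (1 + t/tmax)·exp(−t/tmax) at t = 2 h, for tmax 30, 60, 90 min: 0.092, 0.406, 0.615.
- Triangular curve with peak p and end T, r = (T − 2)²/[T(T − p)], for (p, T) = (0.5, 4), (1.5, 4), (0.5, 8), (1.5, 8) h: 0.286, 0.400, 0.600, 0.692.

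Take the threshold as PG <60 plus 10 minutes (three readings). The tmax 30 curve then reaches it at 1.31, 1.51, 1.67 and 1.89 h from 80, 90, 100 and 120 mg/dl, so it leaves through the third exit. For the other six curves, PG at two hours is:

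| PG₀ | tmax 60 | tmax 90 | (0.5, 4) | (1.5, 4) | (0.5, 8) | (1.5, 8) | Below 70 |
|---|---|---|---|---|---|---|---|
| 80 | 62.2 | 68.5 | 58.6 | 62.0 | 68.0 | 70.8 | 5 of 6 |
| 90 | 66.2 | 74.6 | 61.4 | 66.0 | 74.0 | 77.7 | 3 of 6 |
| 100 | 70.3 | 80.8 | 64.3 | 70.0 | 80.0 | 84.6 | 1 of 6 |
| 120 | 78.4 | 93.1 | 70.0 | 78.0 | 92.0 | 98.5 | 0 of 6 |

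(The 58.6 trace crosses 60 at 1.84 h, too late for three readings by two hours.)

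The table has two limits. All nine traces below 70 are falling, by 6.5–17.9 mg/dl over the second hour; none is flat. And the fall still to come is 8.6–18.5 mg/dl in those nine, against 20–48.5 mg/dl in the traces at 70 or above.

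**The case against.** **The exits differ for a reason.** The 70 mg/dl rule is a recovery criterion after hypoglycemia, and the fourth exit is for subjects who had none. A PG of 60–69 is not hypoglycemia by the protocol's definition, and on arrival treatment is required only below 50. This stands as an explanation of the design. It does not explain why the group given extra insulin has the weaker floor.

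**Stable already does the work.** Staff may well decline to call a falling PG stable. That stands. A reader might take the modelled counts (5, 3, 1 and 0 of six) as the frequency of unsafe discharges, or infer that subjects are sent home with glucose falling. The documents support neither: every trace counted is falling, so the existing condition may already hold it. What the condition does not clearly catch is a level trace at 60–69, and no count of those can be made.

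**The model leaves out the device.** Subjects come off the bionic pancreas only at discharge, and section VI.b.3 lists glucagon dosing to the end of the visit separately from dosing to the end of post-exercise monitoring. By the planning rates, glucagon is available in about 15 of 20 injected visits and automated insulin adjustment in all 20. Both would lessen the fall, so the table is illustrative only.

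**Other protections exist.** An RN or MD supervises throughout the clinic visit, readings are frequent, a snack is made available afterwards, and subjects returning to their pump have recent dosing reviewed. Same-day restarters go through sensor, pump and data-streaming checks, then have alarms at 50 and 55 mg/dl, a glucose-responsive controller and an on-call provider. These limit the risk, but none sets a glucose level for leaving.

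**A 70 floor does not remove residual insulin.** Correct: in the model, subjects released above 70 have the larger fall still to come. The snack and the dosing review have to cover them.

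**Conclusion.** The gap is real and narrow. As written, a subject with a steady PG of 60–69 mg/dl two hours after insulin aimed at 50 mg/dl may be discharged, and the criterion in the other three exits would hold that subject. This follows from the text alone and does not depend on the model. It concerns at most roughly 0–10 of 40 visits. The share of those at a steady 60–69 is unknown and may be very small.

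A reader might infer more from the 4–8 hour clearance time: that two hours is unsafe in itself, or that observation for the full period is needed. The documents do not show that, given the supervision, the running device and the measures at discharge. Nor is the primary endpoint touched, because the dose is given after the post-exercise monitoring period that supplies it. This is a worthwhile, low-cost safety improvement, not a fatal flaw. It assumes that the threshold is the one implied by the exercise stopping rules, and that the figure missing from this section states no separate discharge level.

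**What to change.** In section V.d.v, amend the fourth exit:

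- For an injected subject who has not reached the threshold at two hours, require PG ≥70 mg/dl maintained for 1 hour before discharge or bionic pancreas restart. The hour may fall within the two hours.
- If this is not met at two hours, continue observation and allow oral carbohydrate from that point only. Allowing it earlier would work against the purpose of the dose, which section I.d gives as raising the chance of mild hypoglycemia for breath and sweat samples (Aim 2). Treatment of hypoglycemia per protocol is unchanged.
- Include the time and size of the syringe dose in the dosing review for all injected subjects, including same-day restarters.

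The exit for subjects who reach the threshold after the dose needs no added two-hour minimum. In the same assumed profiles, with 15 minutes allowed for recovery, its 1-hour rule already ends at about 2.0–3.2 h.

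The cost is a few sentences in an amendment and somewhat longer observation at some of the roughly 0–10 visits. A subject who stays at or above 70 mg/dl through the second hour still leaves at two hours. Sample size, power and type I error do not change.

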- Date of diabetes diagnosis

899

- Medical, surgical, and social history, allergies, and review of systems relevant to inclusion and exclusion criteria

900

- Medications (prescription and non-prescription) and date of last change in medication regimen

901

- Duration of insulin pump use

902

- Type of insulin used in pump

903

- Insulin regimen (basal rate, sensitivity factor, and carbohydrate ratio)

904

- Average total daily dose of insulin in the last 30 days as available

905

- Usage of CGM (type of CGM, days per month worn, usage of data, whether insulin is dosed based on CGM alone, alarm settings)

906

907

- 908 • Height and weight
- 909 • Blood pressure
- 910 • EKG if applicable
- 911 • Hemoglobin A1c
- 912 • Hemoglobin
- 913 • Urine HCG (pre-menopausal females)
- 914 • Fractionated plasma metanephrines (if indicated by history)

915

916 **VI. a. 2. During the Outpatient Period of Both Study Arms:**

- 917 • CGMG (CGM glucose) every five minutes from the Dexcom CGM
- 918 • All fingerstick BG measurements taken by the subject (meter download)
- 919 • Insulin total daily dose
- 920 • Glucagon total daily dose
- 921 • Timing of meal announcements and size of meals announced
- 922 • Timing and doses of glucagon boluses
- 923 • Time subjects were not under bionic pancreas control
- 924 • List of technical faults associated with the bionic pancreas including cause and resolution

925

926 **VI. a. 3. During the Exercise Visit:**

- 927 • Plasma BG measurements every 10 minutes, every 5 minutes when BG < 80 mg/dl, or every 20 minutes
- 928 when exercise is complete and BG > 120 mg/dl
- 929 • Time from start of exercise to first glucose measurement < 60 mg/dl
- 930 • Grams of oral carbohydrates given to the subject to treat hypoglycemia
- 931 • Timing of exercise and duration

932

933 **VI. b. Study Endpoints**

934

935 **VI. b. 1. Primary endpoint analysis (considers only the exercise and post-exercise monitoring period)**

936 Number of subjects discordant between insulin-only and bionic pancreas visits for reaching a PG <60

937 mg/dl (using the YSI) for >2 consecutive measurements during the exercise and post-exercise

938 monitoring period; only the first such event will be counted for this analysis

939

940 **VI. b. 2. Secondary endpoint analyses (during the exercise and post-exercise monitoring period)**

- 941 • Duration of plasma glucose <60 mg/dl
- 942 • Nadir plasma glucose
- 943 • Area over the plasma glucose curve and < 60 mg/dl

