- 989 • All of following metrics will be generated from any fingerstick data available (downloaded from the
990 subjects meter) during the outpatient bionic pancreas and usual care periods.
- 991 • Mean number of daily BG measurements
- 992
- 993

994 **Analysis of the Effect of Glucagon During the In-clinic Experiment**

995 We will assess the incremental effect of glucagon in the context of automated insulin delivery by the bionic
996 pancreas in preventing hypoglycemia during exercise in the fasted state. The primary outcome will be
997 derived from the plasma glucose values collected throughout the exercise visits. Mean glucose,
998 time-in-range, and time in hypoglycemia measures will be separately calculated using both plasma
999 glucose values and CGM glucose values for the in-clinic exercise experiments and both will be
1000 reported. For the primary outcome we will compare the proportions of patients having at least one
1001 hypoglycemia event between the bi-hormonal and insulin-only bionic pancreas arms. A hypoglycemia event is
1002 defined as an event with PG <60 mg/dl for more than two consecutive measurements.

1003 In the crossover design, each subject will serve as their own control and the hypoglycemia event is considered
1004 to be correlated within the same patient. We will apply a two-sided exact McNemar's test to compare

1005 hypoglycemia rates between the bi-hormonal and insulin-only bionic pancreas arms. We use a conservative
1006 threshold for p-value <0.025 as indication of statistical significance.

1007 In the case of a subject who withdraws from the study after participating in only one of the in-clinic experiments
1008 we will use multiple imputations to replace the missing data and perform a sensitivity analysis comparing the
1009 result using multiple imputations to the result obtained including only subjects that have completed both of the
1010 in-clinic visits.

1011 For the time from the start of exercise to first PG <60 mg/dl endpoint we will perform survival analysis using the
1012 Kaplan-Meier method and will compare arms with a Cox Proportional Hazards model accounting for within patient
1013 correlations.

1014
1015 **Analysis of Outpatient Outcomes**

1016
1017 For the outpatient run-in period only outcomes based on CGM glucose values will be reported. The
1018 primary analysis of the designated endpoints will be calculated on an intention-to-treat basis, including data

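### The primary endpoint can score a visit as free of hypoglycemia because protocol-required carbohydrate ended the low before a third reading; probably uncommon, but one visit can decide the test

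*Combined protocol and SAP*

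**What the plan says.** **Endpoint.** Section VI.b.1 counts PG below 60 "mg/dl (using the YSI) for >2 consecutive measurements during the exercise and post-exercise" monitoring period, and only the first such event. The analysis section on the in-clinic effect of glucagon repeats this: an event is "defined as an event with PG <60 mg/dl for more than two consecutive measurements". Neither place mentions PG below 50 or carbohydrate treatment.

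**Conduct.** Section V.d.v, Exercise Visits, gives two glucose-based reasons to stop the walk. One is a single low value: "Subjects reach a PG of 50 mg/dl or lower". The other is "Subjects reach a PG of < 60 mg/dl but > 50 mg/dl for three consecutive measurements taken" every 5 minutes, followed by a choice to treat. A separate line makes carbohydrate compulsory: "If PG is < 50 mg/dL, exercise will be terminated and subjects will be required to treat with" carbohydrate. Below 80 mg/dl, sampling is every 5 minutes during and after exercise, and it continues after treatment.

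**Treatment after exercise.** The carbohydrate rule adds: "Repeat treatments will be given at 15 minute intervals as long as hypoglycemia continues". The post-exercise text instead lets subjects who have reached the hypoglycemia threshold treat "with oral carbohydrates at their discretion during this time to maintain their blood glucose". For the period after the later insulin injection it says "hypoglycemia will be treated per protocol".

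**Test and planning.** The test is a two-sided exact McNemar test with a 0.025 threshold and 20 subjects. Section VI.c expects event rates of 25% (bi-hormonal) and 75% (insulin-only).

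**The concern.** Aim 1 asks whether glucagon prevents hypoglycemia. A visit in which PG fell far enough for carbohydrate to be compulsory is not one in which the device prevented hypoglycemia. Yet if the carbohydrate works before a third low reading, the visit enters the primary test as a success. The deeper excursion is scored better than a shallower untreated one.

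The direction is open. A missed low in the insulin-only arm works against glucagon, and one in the bi-hormonal arm works in its favour. Nadir PG, duration and area below 60, and time to first PG below 60 would all show the visit, but none of them enters the McNemar test.

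**Working it through.** **1. How three sequences are scored** (readings 5 minutes apart, each run preceded by a reading of 60 or more)

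| Readings | Required carbohydrate | Consecutive readings <60 | Primary score |
|---|---|---|---|
| 59, 58, 57 | no | 3 | event |
| 58, 49, 62 | after 49 | 2 | no event |
| 58, 49, 56 | after 49 | 3 | event |

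The third row shows that required treatment does not by itself remove an event, because readings after treatment still count.

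**2. What an escape requires.** There are three ways to have a PG below 50 but fewer than three low readings.
- Low reading of 50-59, then below 50, then 60 or more: a rise of more than 10 mg/dl in 5 minutes, which is above 2 mg/dl/min.
- Below 50, then straight to 60 or more: the same bound on the rise.
- Below 50, then another value below 60, then 60 or more: if a reading of 60 or more came 5 minutes earlier, the fall exceeded 10/5 = 2 mg/dl/min. If the earlier reading was 80 or more and came 10 minutes before, the fall exceeded 30/10 = 3. The only exception is a first YSI reading already below 50.

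Now take a straight-line fall and assume PG does not rise for at least 5 minutes after carbohydrate. At falls of 2 mg/dl/min or less, the first low reading cannot be below 50, so the treated reading is at least the second low one. The reading 5 minutes later is still low, which makes three. No visit escapes. With a 10-minute lag, two further readings are low and no visit escapes at any rate of fall. These lags and rates are assumptions; the documents give none.

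**3. The plan's power.** Take 25% and 75%, and 5% of bi-hormonal events not shared with insulin-only.
- Both arms: 0.25 × 0.95 = 0.2375
- Bi-hormonal only: 0.25 × 0.05 = 0.0125
- Insulin-only arm only: 0.75 − 0.2375 = 0.5125
- Neither: 1 − 0.2375 − 0.0125 − 0.5125 = 0.2375

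Sum the trinomial probabilities of all discordant counts (b, c), N=20, for which the exact two-sided binomial p is below 0.025. This gives 0.898, against the stated 90%. The other rows of the table (25, 20, 15, 10 and 1%) give 0.750, 0.784, 0.819, 0.857 and 0.933. All six agree with the plan.

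**4. What one visit can do.** With b+c discordant pairs and c the smaller count, p = 2 × P(Bin(b+c, 0.5) ≤ c).

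| Split | p | One insulin-only event fewer | p |
|---|---|---|---|
| 7-0 | 0.0156 | 6-0 | 0.031 |
| 9-1 | 0.0215 | 8-1 | 0.039 |
| 11-2 | 0.0225 | 10-2 | 0.039 |

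Summing over the four planned cells:
- Significant, but not after one bi-hormonal event is added to a subject with an insulin-only event (b falls by one): 8.1% of trials.
- Significant, but not after that event is added to a subject with no event (c rises by one): 19.8%.
- Not significant, but significant after one added insulin-only event: 7.0%.

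Section VI.c expects 95% of subjects with hypoglycemia on glucagon to have it without glucagon as well, so the first placement is the more plausible one.

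**5. Power if the composite is adopted.** Let gi and gb be the shares of visits now scored no event that become events (insulin-only, bi-hormonal). Then p10′ = (1−gb)(0.5125 + 0.2375·gi) and p01′ = (1−gi)(0.0125 + 0.2375·gb). The shares are assumed.
- gi=0.05, gb=0: cells 0.5244 and 0.0119, power 91%.
- gi=0, gb=0.05: cells 0.4869 and 0.0244, power 80%.
- Both 0.05: cells 0.4982 and 0.0232, power 82%.
- Added events equal to 5% of counted events in each arm (gi = 0.0375/0.25 = 0.15, gb = 0.0125/0.75 = 0.0167): cells 0.5390 and 0.0140, power 92%.

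The 80% case is demanding. It adds 0.05 × 75 = 3.75 points to a 25% rate, or 15% more bi-hormonal events, with none in the other arm.

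**The case against.** The best defence is that the plan's rule is complete and was fixed in advance. It requires a sustained, confirmed low, which is a legitimate choice; the composite would let one unconfirmed reading decide a subject's outcome. The exercise was chosen to be mild, so falls above 2 mg/dl/min should be unusual. Secondary endpoints show rescued lows, and time to first PG below 60 has its own Kaplan-Meier and Cox analysis. Fragility to one visit belongs to any exact test on 20 pairs and says nothing about how often this case arises.

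Most of that stands. A reader might infer that the plan leaves such visits unscored; it does not. A reader might also infer that the stated power is too high because 25% and 75% describe a broader event. The analysis section defines the event just before the power section uses the rates, so the natural reading is that they refer to the three-reading event. The looser definition under Aim 2 (any BG below 60) concerns sample collection.

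What does not fall away is the ordering: a visit needing compulsory rescue can score better than one that did not, in the only test that decides the trial.

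**Conclusion.** The point holds as a minor one. The definition gives every visit a score, but in a narrow case that score is perverse: required treatment removes the outcome it was a response to. The case is probably uncommon, by the bound above and under the assumed straight-line model with a carbohydrate lag of at least 5 minutes.

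It would be tempting to say that the rule biases the comparison toward glucagon. The documents do not support that, since they give neither a frequency nor a split by arm, and a missed low in either arm is possible. Nor do they show the 90% power to be wrong; it reproduces.

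The reason to act is leverage. At the planned rates one re-scored visit can remove significance in about 8% of trials (20% under the less plausible placement) or create it in 7%. Those figures are conditional on such a visit occurring.

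**What to change.** First reconcile the passages in V.d.v that set the trigger. Exercise stops at 50 or lower, but carbohydrate is required only below 50. After exercise, one passage repeats treatment while hypoglycemia continues and another leaves it to the subject. No treatment rule is proposed here; the endpoint only needs an unambiguous trigger.

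Then, before outcomes are seen, define the primary event as either PG below 60 on more than two consecutive measurements, or a PG within the exercise and post-exercise monitoring period at which the protocol requires carbohydrate. Report the current definition as a pre-specified sensitivity analysis. If the sponsor prefers to keep the current primary, the composite should at minimum be that sensitivity analysis. State which definition the 25% and 75% describe.

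The cost is wording. PG values and carbohydrate grams are already collected (VI.a.3), and VI.b.3 already uses the time at which treatment is required. There are two downsides: a single unconfirmed reading can decide a subject's outcome, and power can move either way, by little if the case is rare. Reporting both definitions shows how much either matters.
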